9.4.1 General Approach

Data will be summarized using mean, standard deviation, median, minimum and maximum for continuous variables and count and percentages for categorical variables. For laboratory data, 10th and 90th percentiles will be used instead of minimum and maximum. Mean plots and boxplots will be used to display summary statistics over time for continuous variables. For comparing the demographic and laboratory variables between cohorts at a given time point, exact two-tailed Wilcoxon test will be used to compare the two cohorts for continuous variables, due to small sample size and indication of nonnormality, and two-tailed Fisher's exact test for categorical variables. For estimating proportions, Clopper-Pearson method will be utilized. For investigating the change in hematology and chemistry parameters collected over time, generalized linear mixed model with random effects may be utilized to compare the cohorts. Confidence level will be at least 95% for estimation and significance level will be at most 5% for test of hypothesis, respectively. There will be no adjustments for multiple intervals or testing.

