9.4.4 Safety Analyses

Safety evaluations will be based on the incidence, severity, and type of AEs. Safety variables will be tabulated and presented for all subjects in the safety population. All tests will use a 5% significance level, i.e., p-values < 0.05 will be considered significant, and for estimation a 95% confidence level will be used.

Symptoms and toxicities will be listed and the counts and proportion computed by dose cohort. Clopper-Pearson method will be used to estimate confidence intervals (or upper bound) around the estimates of these proportions and Fisher's exact test to compare the proportions between dose cohorts. Summary statistics will be presented for continuous laboratory safety parameters. Data will be presented using appropriate graphical tools to help compare the different dose cohorts. The exact Wilcoxon test will be used to compare between dose cohorts at a given time point or area under the curve for variables collected over time (e.g., laboratory parameters). For area under the curve, the average will be taken to adjust for shortened length of follow-up for dropouts. Linear mixed model with random intercept may be considered to analyze data collected over time to account for correlation of data from the same subject. This method provides another perspective of comparing the treatment cohorts as area under the curve due to being a summary statistic may miss important features of the data that mixed model may detect. The generalized linear mixed model can handle continuous, binary and count data. To measure strength of correlation between continuous variables, the Pearson correlation (or Spearman rank correlation for variables not distributed normally) will be used. Analyses will be done using SAS version 9.4.

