3.3. Study Definitions and Derived Variables

Baseline Value

The baseline value will be defined as the last value obtained prior to the administration of study product.

Post-Baseline Value

Post-Baseline values refer to measurements and assessments collected after the first administration of study product.

Change From Baseline

Change from baseline will be calculated as: (Post-Baseline value) – (Baseline Value). If the baseline value is not available or is indeterminant, change from baseline will be undefined.

Analysis Day

For clinical laboratory data, summaries will be generated by nominal time point corresponding to the study visit day (e.g., Baseline and Day 5). For such summaries, the data point collected within the visit window (see [Table 2](#)) will be used as the data point for the time point. In the case of multiple records within a specific visit window, the value that is closest to the targeted study day will be used in the summaries. If observations have the same distance to the scheduled assessment, the latest one will be used. Data from supplemental and/or unscheduled visits may be used to provide a measurement for a time point, if appropriate.

All the recorded data will be included in listings.

Days on Study

The number of days the participant was on study will be calculated as follows:

(Protocol completion date or early termination date) – (Enrollment date) + 1

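### The Protocol's only committed between-cohort test of laboratory values leaves out each infant's pre-dose value, and the SAP carries neither that test nor a note that it was dropped

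*Protocol*

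**What the plan says.** Protocol 9.4.1 is definite for continuous variables: "For comparing the demographic and laboratory variables between cohorts at a given time point, exact two-tailed Wilcoxon test will be used". Protocol 9.4.4, with matching text in 9.4, says: "The exact Wilcoxon test will be used to compare between dose cohorts at a given time point or area under the curve". Neither mentions the pre-dose value. Protocol 9.4.1 also sets the error rate ("significance level will be at most 5% for test of hypothesis") and adds: "There will be no adjustments for multiple intervals or testing".

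Baseline could enter a between-cohort comparison at one point only. Protocol 9.4.1 says that for "investigating the change in hematology and chemistry parameters collected over time, generalized linear mixed model with random effects may be utilized". Protocol 9.4 and 9.4.4 describe a random-intercept model in similarly optional terms. No model terms are given.

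SAP 3.3 defines baseline ("The baseline value will be defined as the last value obtained prior to the administration of study product") and change from it. SAP 9.6 displays that change by dose level in Tables 24 and 26 and Figures 6 and 7. These displays carry no between-dose estimate or interval. The SAP names no Wilcoxon test, Fisher test or mixed model, yet SAP section 15 reports no changes to the planned analyses.

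**The concern.** The 10 and 20 mg/kg cohorts are enrolled one after the other, without randomisation (Protocol 4.1; SAP 4.4.3), and safety assays run in each site's local laboratory (Protocol 8.3). Infants are at most 2 days old at enrolment, an age at which some of these values move quickly. In Appendix A the Grade 1 range for low ANC starts at 5,000 at 1 day of age or less and at 1,500 at 2 to 7 days. The cohorts could therefore start from different levels for reasons unrelated to dose. A raw Day 5 comparison passes part of such a difference into the dose contrast, where it can mimic or hide an effect on neutrophils or creatinine, the two toxicities named in Protocol 2.3.1. If the pre-dose value predicts the Day 5 value, leaving it out also costs precision in a comparison of 8 against 8.

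**Working it through.** **The plan's own figure.** The documents give no power, effect size, SD or correlation for the laboratory comparison. Their only precision figure is the exposure interval in Protocol 9.2: mean ± t(0.975, 7) × SD/√n = 24,000 ± 2.3646 × 8,000/√8 = 24,000 ± 6,688, or 17,312 to 30,688. It reproduces, but it does not bear on laboratory values.

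**Inputs from the documents.** 8 infants per cohort (Protocol 1.1); two-sided 5% (9.4.1); laboratory draws scheduled on Days 1 and 5 only (4.1).

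**Assumed inputs.** Bivariate normal values with SD 1; baseline-Day 5 correlation ρ from 0 to 0.8; true dose shift of 0 or 1 SD; true baseline difference D of 0 or 0.5 SD.

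**Bias.** If the difference regresses in line with ρ, the raw Day 5 contrast is biased by ρ × D. For D = 0.5 this is 0.25, 0.35 and 0.40 SD at ρ = 0.5, 0.7 and 0.8. ANCOVA removes it. If the difference persists in full, as a laboratory offset would, raw bias is 0.50 SD and ANCOVA keeps (1 − ρ) × D = 0.25, 0.15 and 0.10 SD.

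**Precision.** The raw SE is √(2/8) = 0.50 SD. ANCOVA multiplies the variance by about (1 − ρ²) × 13/12, giving an SE of 0.52, 0.50, 0.45, 0.37 and 0.31 SD at ρ = 0, 0.3, 0.5, 0.7 and 0.8. A change score multiplies it by 2(1 − ρ), so it gains only above ρ = 0.5, and it carries a bias of −(1 − ρ) × D when the difference regresses.

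**Simulation.** The exact 8 v 8 rank-sum test rejects at a rank sum of 49 or less in either cohort, with true size 4.99%. With 200,000 data sets per setting:

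| ρ | 0 | 0.3 | 0.5 | 0.7 | 0.8 |
|---|---|---|---|---|---|
| Power, 1-SD shift: raw Wilcoxon | 44% | 44% | 44% | 44% | 44% |
| Power: Wilcoxon on change | 25% | 34% | 44% | 65% | 81% |
| Power: ANCOVA | 43% | 47% | 54% | 71% | 84% |
| Power: rank ANCOVA (t reference) | 42% | 45% | 51% | 63% | 74% |
| False positives, D = 0.5 regressing: raw | 5.0% | 5.8% | 7.3% | 9.7% | 11.2% |
| Same: ANCOVA | 5.0% | 5.0% | 4.9% | 5.0% | 5.0% |
| False positives, D = 0.5 persisting: raw | 15% | 15% | 15% | 15% | 15% |
| Same: ANCOVA | 14% | 9.8% | 7.8% | 6.6% | 5.9% |

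**Chance imbalance.** With identical populations the raw test rejects 5.0% overall. Among data sets with an observed baseline difference of 0.4 to 0.6 SD, it rejects 4.8, 4.3 and 3.6% at ρ = 0.5, 0.7 and 0.8. Differences above 0.5 SD arise by chance about 32% of the time at this size, but the test's 5% already covers them.

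**The area-under-the-curve option.** With two scheduled draws, the time-averaged area is the mean of the pre-dose and Day 5 values. That halves the dose effect and puts the pre-dose value into the outcome. Power for a 1-SD shift is 16 to 20% at ρ from 0.3 to 0.8, so this option is not a baseline adjustment.

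**The case against.** The strongest reply is that nothing turns on this test. Cohort 2 dosing uses mean exposure and Grade 3 or 4 AEs or SAEs (Protocol 6.1.3, 9.4.6). Halting uses SAEs and graded AEs (7.1.1, 7.1.2). The safety endpoints are Grade 3 AEs, Grade 4 AEs and SAEs. Infants with any baseline laboratory value of Grade 1 or higher are never dosed, which limits imbalance in the adverse direction. All of this stands and keeps the point modest.

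A reader might infer that the plan as a whole ignores baseline. It does not: there is the optional model, the SAP's change-from-baseline displays, and creatinine grading that refers to the infant's own baseline. The gap is confined to the committed test.

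A reader might also infer that small cohorts alone inflate the error rate through chance imbalance. The working shows otherwise; inflation needs a true difference between the cohorts, and the documents give no evidence of one.

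It is also fair to say that the SAP, whose preface claims to cover all safety analyses by the data centre, contains no such test to replace. But SAP section 15 declares no change, so the Protocol's commitment has not been withdrawn.

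**Conclusion.** The point holds in a limited form. The one definite between-cohort laboratory test omits a pre-dose value that is already collected, in cohorts that are not randomised, and the SAP leaves the test's status unclear.

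The size depends on a correlation that the documents do not give. At ρ of 0.3 or below the power gain is negligible, and at 0 there is a slight loss, so the documents do not support an unconditional claim that power is lost. Low correlation is plausible for ANC, given the steep age change in its grading limits. At 0.5 to 0.8 ANCOVA gains about 10 to 40 percentage points for a 1-SD shift; the rank version gains about 7 to 30.

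The false-positive figures require a true 0.5-SD baseline difference, and the return to about 5% requires that difference to regress. Normality and the absence of baseline truncation are simplifications. Nor is adjustment a cure for confounding: other differences between sequential cohorts remain.

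**What to change.** For any between-cohort comparison of Day 5 laboratory values, replace the unadjusted Wilcoxon test in Protocol 9.4, 9.4.1 and 9.4.4 with a baseline-adjusted one, and put the same sentence in SAP 9.6. Either rank ANCOVA with a permutation p-value, or ANCOVA of the log value on the log baseline, would serve. A simple change score should not be the test. Report the 20 minus 10 mg/kg difference with its 95% CI; on the log scale it back-transforms to a ratio. If rank ANCOVA supplies the p-value, take the interval from the log model. Age at the baseline draw is an optional second covariate, given only 16 infants. The unadjusted test can stay for baseline variables.

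If the sponsor wants description only, add intervals to the change-from-baseline summaries by dose in Tables 24 and 26, say that no between-cohort test will be done, and record the dropped tests in SAP section 15.

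The cost is a sentence or two in each document and a few lines of code, with no new data. The statistical price is one model degree of freedom (13 residual instead of 14), or two if age is added.

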9.4.2 Analysis of the Primary Endpoint(s)

Standard noncompartmental techniques will be used to assess pharmacokinetic parameters derived from the full PK profile obtained on Study Day 5 (window: Study Day 4 through Study Day 5). The resource utilized for pharmacokinetic analysis is Phoenix WinNonlin v8.3.1 (or later), Certara USA, Inc. (Princeton, NJ). AUC₁₂ is the primary objective, which will be determined using the linear-log trapezoidal rule. In addition, a population PK analysis may be conducted at the end of the study.

9.4.3 Analysis of the Secondary Endpoint(s)

Secondary objectives include calculation of additional pharmacokinetic parameters other than AUC_{12} , including (but not limited to): AUC_{∞} , C_{max} , $t_{1/2}$, T_{max} , k_e , CL/F , V/F , C_{12h} , and T_{last} . C_{max} will be taken as the maximum observed concentration. T_{max} is the time at which C_{max} occurs. Oral clearance (CL/F) will be calculated as $dose/AUC_{12}$. The elimination half-life ($t_{1/2}$) is a secondary parameter that will be determined using regression analysis of the terminal elimination phase concentration-time points. This will also be accomplished using Phoenix WinNonlin (see [section 9.4.2](#) for additional details).

Grade 3 AEs and 4 AEs and SAEs are also secondary endpoints. See [Section 9.4.4](#) for details of their analyses.

9.4.4 Safety Analyses

Safety evaluations will be based on the incidence, severity, and type of AEs. Safety variables will be tabulated and presented for all subjects in the safety population. All tests will use a 5% significance level, i.e., p-values < 0.05 will be considered significant, and for estimation a 95% confidence level will be used.

Symptoms and toxicities will be listed and the counts and proportion computed by dose cohort. Clopper-Pearson method will be used to estimate confidence intervals (or upper bound) around the estimates of these proportions and Fisher's exact test to compare the proportions between dose cohorts. Summary statistics will be presented for continuous laboratory safety parameters. Data will be presented using appropriate graphical tools to help compare the different dose cohorts. The exact Wilcoxon test will be used to compare between dose cohorts at a given time point or area under the curve for variables collected over time (e.g., laboratory parameters). For area under the curve, the average will be taken to adjust for shortened length of follow-up for dropouts. Linear mixed model with random intercept may be considered to analyze data collected over time to account for correlation of data from the same subject. This method provides another perspective of comparing the treatment cohorts as area under the curve due to being a summary statistic may miss important features of the data that mixed model may detect. The generalized linear mixed model can handle continuous, binary and count data. To measure strength of correlation between continuous variables, the Pearson correlation (or Spearman rank correlation for variables not distributed normally) will be used. Analyses will be done using SAS version 9.4.

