9.4.6 Planned Interim and Early Analyses

The initial oral valacyclovir dose will be 10 mg/kg administered two times daily for 5 days (**Cohort 1**). The target exposure for acyclovir following oral valacyclovir dosing is 36,000 ngxhr/mL with a range of 24,000 ngxhr/mL to 48,000 ngxhr/mL. Upon full accrual of Cohort 1, the PK and safety data will be reviewed. If the mean of observed acyclovir exposures of subjects in Cohort 1 are below 24,000 ngxhr/mL, AND if no Grade 3 or Grade 4 AEs or SAEs are detected in any of the study subjects, then the 8 subjects enrolled in Cohort 2 will receive oral valacyclovir at a dose of 20 mg/kg administered two times daily for 5 days. Alternatively, if the mean of observed acyclovir exposures of subjects in Cohort 1 are above 48,000 ngxhr/mL AND if no Grade 3 or Grade 4 AEs or SAEs are detected in any of the study subjects, then the 8 subjects enrolled in Cohort 2 will receive oral valacyclovir at a dose that has been linearly adjusted downward to target 36,000 ngxh/mL area-under-the-concentration-time curve from 0 to 12 hours (AUC_{12}). The SMC retains the ability to suggest an alternative dose be studied in Cohort 2 if the mean AUC_{12} from Cohort 1 is within but at or near the lower or upper ranges in order to attain an AUC_{12} closer to the 36,000 ngxhr/mL target. After assessment of drug exposure and safety in Cohort 1, eight new subjects will be enrolled in **Cohort 2**, with the dose that these subjects will receive being predicated upon the pharmacokinetic data from Cohort 1.

If the targeted exposure is not achieved in Cohorts 1 and 2 and the safety data are acceptable, it is possible, but not anticipated, that additional dosing cohorts could be recommended based upon the results of subjects in the first two cohorts. If such a recommendation is made, dose selection and subject enrollment and assessment will follow the approach used for Cohort 2.

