10.1.6 Safety Oversight

The DMID Medical Monitor will be responsible for reviewing SAEs in real time and all safety data. The Lead PI will also review the SAEs and AE listings as needed to ensure the safe conduct of this trial.

Safety oversight will be conducted by a Safety Monitoring Committee (SMC) that is an independent group of experts that monitors subject safety and advises DMID. The SMC

members will be separate and independent of study personnel participating in this trial and should not have scientific, financial or other conflict of interest related to this trial. The SMC will consist of members with appropriate expertise to contribute to the interpretation of the data from this trial. The SMC will operate under the rules of a SMC-approved charter that will be written at the organizational meeting of the SMC. The SMC will review AEs and SAEs on a regular and ad hoc basis during the trial.

The SMC will conduct the following reviews:

- After each cohort of 8 subjects has completed dosing and been followed for 42 days.
- Ad hoc meeting:
 - When trial-level halting criteria are met
 - At the request of DMID to review a potential safety concern identified by either the lead PI, DMID Medical Monitor, or protocol team
- A final review meeting to review the cumulative safety data for this trial.

The study will not stop enrolled awaiting the regularly scheduled SMC reviews, although the SMC may recommend temporary or permanent cessation of enrollment based on their safety reviews.

Additional data may be requested by the SMC, and interim statistical reports may be generated as deemed necessary and appropriate by SMC. The SMC may receive data in aggregate and presented by treatment arm. The SMC may also be provided with expected and observed rates of the expected AEs. The SMC will review grouped data in the closed session only. As an outcome of each review/meeting, the SMC will make a recommendation as to the advisability of proceeding with study interventions (as applicable), and to continue, modify, or terminate this trial.

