4.4.5. Selection and Timing of Dose for Each Participant

The shelf-life of valacyclovir oral suspension following preparation is 28 days in the refrigerator between 2°C to 8°C (36°F to 46°F). Study product will be administered by the parent/guardian if participants are at home, or by the hospital staff if participants are in the hospital. Study Cohort 1 will receive valacyclovir at a dose of 10 mg/kg body weight administered two times daily for 5 days. Specific dosing volumes will be provided for each participant based on body weight and valacyclovir oral suspension concentration. Valacyclovir Oral Suspension will be administered into the participant's mouth via an oral dosing syringe. The parent/guardian will be provided with specific dosing, storage, and administration instructions. If the participant vomits or spits up following the dosing, re-dosing for that dose is not allowed.

Dose selection for Cohort 2 will be predicated upon the PK data from Cohort 1. Specifically, the target range of acyclovir exposure is between 24,000 ngxh/mL and 48,000 ngxh/mL. If the mean of observed acyclovir exposures of participants in Cohort 1 is below 24,000 ngxh/mL, AND if no Grade 3 or Grade 4 AEs or SAEs are detected in any of the study participants, then the participants enrolled in Cohort 2 will receive oral valacyclovir at a dose of 20 mg/kg administered two times daily for 5 days. Alternatively, if the mean of observed acyclovir exposures of participants in Cohort 1 is above 48,000 ngxh/mL AND if no Grade 3 or Grade 4 AEs or SAEs are detected in any of the study participants, then the participants enrolled in Cohort 2 will receive oral valacyclovir at a dose that has been linearly adjusted downward to target 36,000 ngxh/mL AUC_{0-12} . If the mean of observed acyclovir exposures of participants in Cohort 1 is within the target range of 24,000 ngxh/mL to 48,000 ngxh/mL, Cohort 2 will not be opened for enrollment unless suggested by the Safety Monitoring Committee (SMC). Based on review of the safety and PK data by the SMC after Cohort 1, it was decided that Cohort 2 would be opened for enrollment and those participants would receive oral valacyclovir at a dose of 20 mg/kg administered two times daily for 5 days.

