6.6. Interim Analyses and Data Monitoring

The initial oral valacyclovir dose will be 10 mg/kg administered two times daily for 5 days (Cohort 1). The target exposure for acyclovir following oral valacyclovir dosing is 36,000 ngxhr/mL with a range of 24,000 ngxhr/mL to 48,000 ngxhr/mL. Upon full accrual and follow-up of Cohort 1, the PK and safety data will be reviewed by the SMC, using the approved report shell. If the mean of observed acyclovir exposures of participants in Cohort 1 are below 24,000 ngxhr/mL, AND if no Grade 3 or Grade 4 AEs or SAEs are detected in any of the study participants, then the participants enrolled in Cohort 2 will receive oral valacyclovir at a dose of 20 mg/kg administered two times daily for 5 days. Alternatively, if the mean of observed acyclovir exposures of participants in Cohort 1 are above 48,000 ngxhr/mL AND if no Grade 3 or Grade 4 AEs or SAEs are detected in any of the study participants, then the participants enrolled in Cohort 2 will receive oral valacyclovir at a dose that has been linearly adjusted downward to target 36,000 ngxh/mL AUC₁₂. The SMC retains the ability to suggest an alternative dose be studied in Cohort 2 if the mean AUC₁₂ from Cohort 1 is within but at or near the lower or upper ranges in order to attain an AUC₁₂ closer to the 36,000 ngxhr/mL target. Based on review of the safety and PK data by the SMC after Cohort 1, it was decided that Cohort 2 would be opened for enrollment and those participants would receive oral valacyclovir at a dose of 20 mg/kg administered two times daily for 5 days.

If the targeted exposure is not achieved in Cohorts 1 and 2 and the safety data are acceptable, it is possible, but not anticipated, that additional dosing cohorts could be recommended based upon the results of participants in the first two cohorts. If such a recommendation is made, dose selection and participant enrollment and assessment will follow the approach used for Cohort 2.

The SMC will also conduct ad hoc meetings if trial-level halting criteria are met or at the request of DMID to review a potential safety concern identified by either the lead PI, DMID Medical Monitor, or protocol team. Additional data may be requested by the SMC, and interim statistical reports may be generated as deemed necessary and appropriate by the SMC.

There are no other planned interim analyses.

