14.2 Pharmacokinetic Data

Not Applicable. Please see the PK analysis plan.

14.3 Safety Data**14.3.1 Displays of Adverse Events****Table 15: Overall Summary of Adverse Events, Safety Population**

Participants ^a with	10 mg/kg (N = xx)		20 mg/kg (N = xx)		All Participants (N = xx)	
	n	%	n	%	n	%
At least one unsolicited adverse event	x	x	x	x	x	x
At least one related unsolicited adverse event	x	x	x	x	x	x
Mild (Grade 1)	x	x	x	x	x	x
Moderate (Grade 2)	x	x	x	x	x	x
Severe (Grade 3)	x	x	x	x	x	x
Life-Threatening (Grade 4)	x	x	x	x	x	x
At least one severe (Grade 3) or higher unsolicited adverse event	x	x	x	x	x	x
Related	x	x	x	x	x	x
Unrelated	x	x	x	x	x	x
At least one serious adverse event	x	x	x	x	x	x
At least one related, serious adverse event	x	x	x	x	x	x
At least one adverse event leading to early termination	x	x	x	x	x	x
Note: N = Number of participants in the Safety Population.						
^a Participants are counted once for each category regardless of the number of events.						

Table 16: Summary of Adverse Events by MedDRA System Organ Class and Preferred Term, and Dose Level, Safety Population

MedDRA System Organ Class	MedDRA Preferred Term	10 mg/kg (N=X)			20 mg/kg (N=X)			All Participants (N=X)		
		n (%)	95% CI ^a	m	n (%)	95% CI ^a	m	n (%)	95% CI ^a	m
Any SOC	Any PT	x	x	x	x	x	x	x	x	x
[SOC 1]	Any PT	x	x	x	x	x	x	x	x	x
	[PT 1]	x	x	x	x	x	x	x	x	x
	[Etc.]	x	x	x	x	x	x	x	x	x
[SOC 2]	Any PT	x	x	x	x	x	x	x	x	x
	[PT 1]	x	x	x	x	x	x	x	x	x
	[Etc.]	x	x	x	x	x	x	x	x	x
Etc	Etc	x	x	x	x	x	x	x	x	x
Notes: N = Number of participants in the Safety Population. n = Number of participants reporting event. m = Total frequency of events reported. A participant is only counted once per PT. ^a Exact Clopper-Pearson Confidence Interval.										

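### If 20 mg/kg was opened by the written escalation rule, Cohort 1 has no Grade 3/4 AEs or SAEs by selection, so the between-dose difference and the pooled percentage for these endpoints are biased

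*Protocol*

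**What the plan says.** Protocol 9.4.3 states that "Grade 3 AEs and 4 AEs and SAEs are also secondary endpoints" and sends their analysis to 9.4.4. There, AE proportions are computed by dose cohort with Clopper-Pearson intervals, and Fisher's "exact test to compare the proportions between dose cohorts" is applied at the 5% level.

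Protocol 9.4.6 allows the increase to 20 mg/kg when the Cohort 1 mean exposure is below 24,000 ng·h/mL "AND if no Grade 3 or Grade 4 AEs or SAEs are detected in any of the study subjects". SAP 6.6 repeats the condition: "AND if no Grade 3 or Grade 4 AEs or SAEs are detected in any of the study participants". Neither limits it to drug-related events.

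There is a second route. Protocol 6.1.3 says that if the mean is inside the target range, Cohort 2 opens only at the Safety Monitoring Committee's (SMC's) suggestion. Protocol 9.4.6 adds: "The SMC retains the ability to suggest an alternative dose be studied in Cohort 2 if the mean" AUC12 is in range but close to a limit. No zero-event condition is written for this route.

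SAP 4.4.5 records that after SMC review "it was decided that Cohort 2 would be opened for enrollment and those participants would receive oral valacyclovir at a dose of 20 mg/kg" twice daily. It gives neither the route nor the Cohort 1 event count.

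SAP Appendix 1, Table 15 has the row "At least one severe (Grade 3) or higher unsolicited adverse event" and rows for SAEs, each with n and % for 10 mg/kg, 20 mg/kg and All Participants.

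**The concern.** The variable that decides whether the 20 mg/kg cohort exists is the one later compared and pooled across the cohorts. On the escalation branch, any Cohort 1 result other than zero would have prevented that step. The 10 mg/kg column can then only read zero, the difference can only point towards more events at 20 mg/kg, and the pooled percentage includes eight infants whose zeros were a condition of the display existing at all. Neither document says this.

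These are the only listed safety endpoints in a study that, by Protocol 9.4, is meant to inform larger dosing and efficacy trials. A reader of Table 15 could take the dose contrast as a toxicity signal, or the pooled percentage as the event rate in treated neonates. Neither reading would be sound.

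**Working it through.** **Inputs.** Eight infants per cohort (Protocol synopsis). Two-sided 95% confidence and 5% tests (Protocol 9.2, 9.4.4). Two-tailed Fisher test: Protocol 9.4.1 says so for demographic and laboratory variables, and I assume the same for AEs. The true per-infant rate p of a Grade 3/4 AE or SAE is not in the documents. I assume 5%, 10% and 20%, equal at both doses, with infants independent.

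**The plan's own figure.** The zero-event upper bound in Protocol Table 5 is 1 − 0.025^(1/n). At n = 8 this gives 0.3694, as printed, and all eleven rows (n = 5 to 15) reproduce.

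**When Cohort 1 is fixed at zero.** Protocol 10.1.6 sets the SMC review "After each cohort of 8 subjects has completed dosing and been followed for 42 days", and SAP 6.6 also places it after follow-up. AEs are collected until four weeks after the last dose, about Day 5 + 28 = Day 33. A review at that point sees the whole reporting window, so passing the condition means X1 = 0 of 8.

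**Consequences given X1 = 0 and X2 ~ Binomial(8, p).**

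- Chance that Cohort 1 meets the condition: (1 − p)^8.
- Expected difference, 20 minus 10 mg/kg: p − 0 = p, where the truth is 0.
- Expected pooled rate: (0 + 8p)/16 = p/2.
- Chance that Cohort 2 shows more events than Cohort 1: 1 − (1 − p)^8. The chance of fewer is 0.

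| | p = 5% | p = 10% | p = 20% |
|---|---|---|---|
| Cohort 1 meets the condition | 66.3% | 43.0% | 16.8% |
| Expected difference (points) | +5 | +10 | +20 |
| Expected pooled rate | 2.5% | 5% | 10% |
| Cohort 2 shows more events | 34% | 57% | 83% |
| Same chance without selection, each way | 24% | 32% | 37% |
| Fisher false-positive rate, given X1 = 0 | 0.00002 | 0.0004 | 0.0104 |
| Fisher false-positive rate, no selection | 0.00002 | 0.0004 | 0.0044 |

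**Fisher's test.** Against 0/8, 4/8 gives p = 0.0769 and 5/8 gives p = 0.0256, so at least five of eight are needed. The conditional false-positive rate is P(X2 ≥ 5). It passes 5% only when the true rate exceeds about 28.9%.

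**Pooling when both cohorts show zero.** The exact upper limit is 20.6% for 0/16, against 36.9% for 0/8. That apparent gain comes entirely from the infants whose zeros were required.

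**The case against.** The strongest reply is that zero by rule is not established. The SMC's in-range route has no written zero-event condition, and the SAP credits the 20 mg/kg decision to SMC review without naming the branch. Review timing also conflicts: Protocol 9.4.6 reviews at full accrual, while Protocol 10.1.6 and SAP 6.6 review after follow-up. On the first timing, a Cohort 1 event could still be added after the decision. This stands, and it makes the point conditional on route and timing.

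Second, a reader might infer that the planned test gives false positives. It does not at plausible rates, as the table shows, and the SAP contains no Fisher test at all.

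Third, a reader might infer that a pooled confidence interval under-covers. The SAP plans no interval for Grade 3 or higher or SAE totals: Table 16 gives intervals by system organ class and preferred term for all grades, and Table 15 gives only n and %. An exact interval on the pooled 16 would in any case cover at least 99.9% of the time at 5%, 10% and 20%. Coverage drops below 95% only once the true rate exceeds about 20.6%.

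Fourth, the study is descriptive with no comparator arm, and the number of exposed infants with an event is a fact worth tabulating. That supports keeping the count. It does not support reading the percentage as a rate.

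**Conclusion.** The point holds in conditional form. If Cohort 2 was opened because the Cohort 1 mean was below 24,000 ng·h/mL, with review after follow-up, Cohort 1 is 0/8 by selection for Grade 3 AEs, Grade 4 AEs and SAEs. At a common true rate p, the dose difference is then overstated by p and the pooled percentage averages half of p. The sizes above rest on assumed rates and on the condition having been met. At 20% that would happen in only about one trial in six. The bias is in the estimates.

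It may be tempting to treat Grade 1–2 AEs and laboratory changes as untouched by the condition. The documents do not support that. Protocol 8.4.1 counts abnormal laboratory findings as AEs, and Appendix A grades them; a creatinine increase of 1.5 to under 2.0 times above baseline is Grade 3, for example. The condition therefore truncates Cohort 1's laboratory changes, and in SAP Table 17 it would place every Cohort 1 AE at maximum Grade 1 or 2. Comparisons of those outcomes need the same caveat.

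**What to change.** Leave the dosing rule as written and change only analysis and reporting:

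- **Protocol 9.4 and 9.4.4:** exclude Grade 3 AEs, Grade 4 AEs and SAEs from the between-cohort Fisher test. The SAP says that it describes all planned safety analyses and has no such test, yet its section 15 reports no changes. Reconcile the two.
- **SAP Table 15:** report these rows by dose, with an exact interval for 20 mg/kg (0/8 would give 0 to 36.9%). Protocol 9.4.4 already plans intervals by cohort, but this table omits them. Keep any All Participants figure as a count, not a rate estimate.
- **SAP Tables 15, 17 and 18:** footnote the escalation condition and the route by which Cohort 2 was opened. Attach the same caveat to comparisons of Grade 1–2 AEs and laboratory change.
- **Review timing:** reconcile Protocol 9.4.6 with Protocol 10.1.6 and SAP 6.6.

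The cost is wording, footnotes, one p-value and one pooled percentage. No data collection changes.
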